From examining multiple configurations, we propose that we need 8 sites with approximately 60 participants per site, on average. This results in a total sample size of 480. Because we believe that recruitment rates are relatively consistent across the 8 outpatient sites, we estimate an effective n of 57. Thus, there is a 3 subject per site penalty for allowing the sites to vary in size. With our proposed sample configuration ($n=60$, $J=8$, effective $n=57$), there is nearly 75% power to uncover main effects of treatment with an effect-size of .45 and relatively small site by treatment variability.

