10.4.1 Main Effect of Treatment (Treatment X Time interaction)

Figure 4 (prepared using software provided by [name]) shows the expected power to uncover a significant overall treatment effect when there are 8 sites ($J=8$), the average treatment effect is .45 ($\delta=.45$) and the variability in this effect size is either small, moderate or large ($\sigma_{\delta}^2=.10$, and .15; as coined by Raudenbush & Liu, 2000). As can be seen in the graph, at the point of 57 subjects per site, power is 87% with small site variability, 75% with moderate site variability, and 64% with high site variability.

FIGURE 4. POWER

[figure not shown]

As can be seen in the graph, site variability in effect-sizes may have a substantial effect on power. If we compare the power calculations above with a simple repeated measures power analysis, we see that if there is no variability in effect-sizes across sites, that we have over 80% power to uncover a considerably smaller standardized effect size. We have used the program described in Hedeker, Gibbons, & Waternaux (1999) to calculate power in the case with no variability of effect-size across sites. In this case, there is over 90% power to uncover a Condition X Time interaction with an effect-size of .25 at the last time of assessment. This estimate assumes 28% attrition over the 12-month post-randomization period, a linear growth curve and minimal residual correlation across time ($\rho = .1$). Power actually increases as the correlation of measures across time increases. It is not uncommon for measures such as those used to test the hypotheses in the trial to show correlations across time in the range of .2 to .4, so power may be better than described here. Clearly, if site variability is smaller than the estimates in the graph above, there is substantially more power. On the other hand, if site variability is higher than the estimates in the graph above, there is substantially less power.

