10.4.3 Probability of Engagement within CTPs

Finally, if we look at the power to uncover differential rates of engagement by condition within a CTP, Figure 6 gives the boundaries for 80% power at the 3 representative CTP sizes, 30, 60, & 90. From examining the graph we can see that at a base rate of engagement in TAU of 40% (for example), that a CTP which had 45 participants per condition (n=90) would need to have an engagement rate in BSFT greater than or equal to 69% to have at least 80% power. The equivalent rates in BSFT for CTPs with 30 and 15 participants per condition are .75 and .86, respectively.

FIGURE 6. P(ENGAGEMENT) PAIRS with 80% Power

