13.0 DISCONTINUATION OF STUDY Interim Analyses

This trial does not meet any of the conditions listed in the Data Safety Monitoring Boards SOP that would require a planned interim analysis for efficacy:

- 1) the trial does not involve over 1000 participants
- 2) treatment is under 6 months in duration
- 3) death or other serious adverse events are not included as efficacy endpoints
- 4) published information supports the efficacy of the experimental treatment
- 5) pharmacological treatment is NOT included in the protocol

There are other factors related to this effectiveness trial's design that lessen the need for an a-priori planned interim analysis. First, this is not a blinded study. Second, the experimental treatment is being compared to the treatment as usual at each site and these sites are established drug treatment centers using established treatment approaches. It is thus highly unlikely that there will be such large effect-sizes that the trial would be stopped early due to the overwhelming efficacy of the proposed experimental treatment. On the other hand, the established research on the proposed experimental treatment does provide substantial evidence of its efficacy in treatment of adolescent problem behavior and drug abuse, making it unlikely that there would be overwhelming efficacy of the treatment as usual, over the experimental treatment. Third, the proposed estimation strategy for this trial directly accounts for the expected variability in effect size across sites by including a random effect for the treatment effect. Note that this variability is expected to be higher than might be seen in efficacy trials due to the variability in treatment as usual across sites. The stability of the statistical model is directly affected by this estimate of variability. It is generally felt that at least 5 sites are necessary to achieve a stable estimate of variability (Brown & Prescott, 1999). Because the primary test includes an interaction by modality (residential vs. outpatient), this would require at least 5 sites in each modality to generate stable estimates of the treatment effect.

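### Section 10.4 attaches 75% power to small site variability, but Section 10.4.1 attaches it to moderate variability, and the random-site power figures allow for no attrition

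*Protocol*

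**What the plan says.** Section 10.4 of the protocol sets the sample size: "we propose that we need 8 sites with approximately 60 participants per site, on average". To allow for unequal sites, "we estimate an effective n of 57", and the difference from 60 is explained in one sentence: "Thus, there is a 3 subject per site penalty for allowing the sites to vary in size". The section then concludes that, with this configuration, "there is nearly 75% power to uncover main effects of treatment with an effect-size of .45 and relatively small site by treatment variability".

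Section 10.4.1 takes the same 8 sites, 57 per site and effect of .45, and reports that "power is 87% with small site variability, 75% with moderate site variability, and 64% with high site variability". It names three levels of variability, but only two variances, .10 and .15, can be read in the text.

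Section 10.4.1 then gives a second calculation, for a repeated-measures design with no variation in effect across sites, which reports over 90% power for an effect of .25. Of that calculation it says: "This estimate assumes 28% attrition over the 12-month post-randomization period".

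**The concern.** The two sections give different power for one design. Under small site variability, power is nearly 75% according to Section 10.4 and 87% according to Section 10.4.1. Both statements are complete prose, so this is not a lost table cell or figure. Section 10.4 is where the number and size of sites are justified, so its sentence is the one most likely to be carried into a report or a board summary.

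Separately, the step from 60 to 57 is attributed wholly to unequal site sizes. The 28% attrition enters only the calculation that leaves out site variability. The calculation that matches the planned analysis, with site as a random effect, assumes full follow-up and does not say so. A reader cannot tell from Section 10.4 which level of variability the 75% belongs to, or that it is a figure before attrition.

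**Working it through.** **Inputs from the protocol.** Sites J = 8 and effective n = 57 per site (Section 10.4); effect d = .45 and variances s² of .10 and .15 (Section 10.4.1); equal allocation within site (30 per group at a site of 60, Section 10.4.2); attrition of 28% (Section 10.4.1).

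**Assumptions.** The small variance is taken as .05. The test is two-sided at .05; Section 10.4 states neither the level nor the sidedness, and Section 13.0 mentions an overall type 1 error of 0.05.

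**Method.** For a multisite trial with a random treatment effect across sites, the test is F with 1 and J − 1 = 7 degrees of freedom and noncentrality

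λ = J·d² / (s² + 4/n), with J·d² = 8 × .45² = 1.62.

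**Step 1: reproduce the plan's figures.** With n = 57, 4/n = .0702.

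| Variability | s² | λ | Power | Section 10.4.1 |
|---|---|---|---|---|
| small | .05 (assumed) | 1.62/.1202 = 13.48 | 88.1% | 87% |
| moderate | .10 | 1.62/.1702 = 9.52 | 75.4% | 75% |
| high | .15 | 1.62/.2202 = 7.36 | 64.5% | 64% |

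All three agree to within about one point. The two rows with legible variances reproduce 75% and 64% without the assumed value. A normal approximation (96/87/77%) and a one-sided t test (95/87/79%) do not reproduce the set. Solving for the variance that gives 75% at n = 57 returns about .10, the moderate value. The figure in Section 10.4 is therefore the moderate-variability figure with the wrong label.

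**Step 2: treat all 28% as lost.** n = 57 × .72 = 41.04, so 4/n = .0975.

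| s² | λ | Power |
|---|---|---|
| .05 | 10.99 | 81.0% |
| .10 | 8.20 | 69.2% |
| .15 | 6.55 | 59.6% |

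Against step 1 the drop is 7, 6 and 5 points.

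**Step 3: a milder loss.** If dropout rises evenly to 28%, the average loss over follow-up is 14% (an assumption). Then n = 57 × .86 = 49.02 and 4/n = .0816.

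| s² | λ | Power |
|---|---|---|
| .05 | 12.31 | 85.1% |
| .10 | 8.92 | 72.7% |
| .15 | 6.99 | 62.4% |

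Here the drop is 2 to 3 points.

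**The case against.** The strongest reply is that this is one wrong adjective. Section 10.4.1 follows at once with all three figures and warns that power falls if site variability is larger. The slip also runs against the plan: for truly small variability, Section 10.4 understates the power in Section 10.4.1. This stands. A reader might infer that the label error inflates the stated power; it does not.

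The reply on attrition is also partly right. Section 10.4.1 does use the 28%, so it is wrong to say that the power section ignores attrition; only the random-site figures omit it. Cutting n to 41 is a complete-case calculation at month 12, whereas Section 10.1.1 specifies maximum likelihood on available data and Section 10.2.1 adjusts for baseline drug use. Suppose linear dropout, so that about 9% are lost by month 4 (n = 51.7), and a baseline correlation r that reduces the 4/n term by the factor 1 − r². Borrowing the .2 to .4 range that Section 10.4.1 gives for correlations across time, power is 87/74/64% at r = .2 and 89/77/66% at r = .4, about the published values. Both inputs are assumptions, but they show that the size of the attrition loss is uncertain.

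Two stronger readings are tempting. Section 13.0 says of the variation in effect across sites: "Note that this variability is expected to be higher than might be seen in efficacy trials". A reader might infer that moderate-to-high variability is the protocol's planning case. The remark is relative and gives no number, so it does not fix one. Section 10.4.3 refers to "80% power at the 3 representative CTP sizes, 30, 60, & 90", and a reader might infer that the effective n should be their harmonic mean, about 49. Those sizes illustrate a within-site engagement graph. Section 10.4 gives its own reason for 57, namely fairly even recruitment across the 8 sites, and nothing in the engagement graph displaces it.

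**Conclusion.** The contradiction is certain and does not depend on any assumption: the same 75% is labelled small in one section and moderate in the next, for identical inputs. Recomputation supports Section 10.4.1, so the label in Section 10.4 is the error.

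The random-site figures are before attrition and are not labelled so. Full loss of 28% gives about 81/69/60%, a lower bound; an average loss of 14% gives about 85/73/62%. These rest on the assumed small variance of .05, a two-sided .05 test, and a simple-difference formula that gives no credit for repeated measures or the baseline covariate. The documents do not establish that power is overstated by any one amount, because the gain from those two features may offset much of the loss. What is established is that one power statement is mislabelled and that the set is incomplete. The design and the sample size are not called into question.

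**What to change.** In Section 10.4, state that power is about 75% with moderate site-by-treatment variability (variance .10), and give 87% for small and 64% for high as in Section 10.4.1, so that the two sections carry the same numbers. Label all three, in both sections, as before attrition, and print the variance used for small.

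Add one sentence with the attrition-adjusted range: about 81/69/60% if all 28% are treated as lost, described as a lower bound because the mixed model uses partial follow-up and a baseline covariate, and about 85/73/62% at an assumed average loss of 14%.

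The cost is protocol wording only. Enrolment, design and analysis do not change. The stated power becomes clearer and, once attrition is shown, somewhat less favourable.

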10.4.1 Main Effect of Treatment (Treatment X Time interaction)

Figure 4 (prepared using software provided by [name]) shows the expected power to uncover a significant overall treatment effect when there are 8 sites ($J=8$), the average treatment effect is .45 ($\delta=.45$) and the variability in this effect size is either small, moderate or large ($\sigma_{\delta}^2=.10$, and .15; as coined by Raudenbush & Liu, 2000). As can be seen in the graph, at the point of 57 subjects per site, power is 87% with small site variability, 75% with moderate site variability, and 64% with high site variability.

FIGURE 4. POWER

[figure not shown]

As can be seen in the graph, site variability in effect-sizes may have a substantial effect on power. If we compare the power calculations above with a simple repeated measures power analysis, we see that if there is no variability in effect-sizes across sites, that we have over 80% power to uncover a considerably smaller standardized effect size. We have used the program described in Hedeker, Gibbons, & Waternaux (1999) to calculate power in the case with no variability of effect-size across sites. In this case, there is over 90% power to uncover a Condition X Time interaction with an effect-size of .25 at the last time of assessment. This estimate assumes 28% attrition over the 12-month post-randomization period, a linear growth curve and minimal residual correlation across time ($\rho = .1$). Power actually increases as the correlation of measures across time increases. It is not uncommon for measures such as those used to test the hypotheses in the trial to show correlations across time in the range of .2 to .4, so power may be better than described here. Clearly, if site variability is smaller than the estimates in the graph above, there is substantially more power. On the other hand, if site variability is higher than the estimates in the graph above, there is substantially less power.

10.4.2 Post Hoc Analysis of Individual CTPs

When examining the distribution of effect sizes across sites, it may be useful to examine the hypotheses within sub-samples. The smallest planned sub-sample is the site (or CTP). For simple comparisons between BSFT and TAU within a CTP, the following graph (Figure 5) shows the relationship between effect size and the sample per group (treatment and TAU) necessary to have at least 80% power within a CTP. Note that this effect size is measured as the simple standardized difference. For CTPs with 60 (or 30 per group, there is 80% power to uncover a standardized effect size of .72.

[figure not shown]
FIGURE 5. REQUIRED CTP N BY EFFECT SIZE

10.4.3 Probability of Engagement within CTPs

Finally, if we look at the power to uncover differential rates of engagement by condition within a CTP, Figure 6 gives the boundaries for 80% power at the 3 representative CTP sizes, 30, 60, & 90. From examining the graph we can see that at a base rate of engagement in TAU of 40% (for example), that a CTP which had 45 participants per condition (n=90) would need to have an engagement rate in BSFT greater than or equal to 69% to have at least 80% power. The equivalent rates in BSFT for CTPs with 30 and 15 participants per condition are .75 and .86, respectively.

FIGURE 6. P(ENGAGEMENT) PAIRS with 80% Power

11.0 DATA MANAGEMENT AND PROCEDURES

11.1 Data Management

In general, data management centers (DMC) of participating nodes will ensure that design, development, validation and implementation of data acquisition systems, independent of the data-model, are in compliance with guidelines and SOPs set forth by the Data Management and Analysis subcommittee (DMAS) of the CTN.

11.2 Design and Development

The lead node will generate and distribute the data-dictionary and sample case report forms (CRFs) to each of the DMCs.

This includes screening and assessment measures, process measures, and tracking measures developed for the study.

The design will incorporate elements of normalized database-design, data-integrity, data-validation, change control, accountability, electronic security and report-generation in each of the acquisition systems.

This includes logical consistency checks, range checks, and handling of missing data.

Each DMC will be responsible for reliability and consistency of their systems and will ensure thorough developer- and user-level testing for completeness and accuracy. Test-data sets shall be provided by the lead-node. The systems need to have adequate backup, recovery and contingency measures for handling of electronic data. As per Federal regulations, the DMC will ensure that any identifying information, if acquired, is stored, both physically and logically, independent of study data. Adequate security measures will be adopted in each Node to only allow authorized access to data-systems.

11.3 Data Acquisition and Entry

Each DMC will ensure timely collection and entry of paper or electronic data in accordance with the requirement of various CRFs. Adequate quality control procedures will be adopted to ensure completeness and accuracy of hardcopies and electronic data. The DMC will establish a regular feedback loop with the study sites (CTPs), via reports and other modes of communication, to ensure quality assurance. In addition, procedures need to be laid out for reconciliation and clean up of collected data. Paper and/or electronic audit-trails with date/time stamps will be maintained to account for any subsequent changes.

11.4 Data Transfer

The DMC will periodically transfer study data to NIDA in a timely and secure manner as per the DMAS guidelines. Corrections based on feedback from the agency will be promptly implemented and will be reflected in subsequent downloads. Periodic summary and detailed study-data reports as specified by the lead-node will be provided by each of the DMCs.

The data-acquisition system for clinical data will be largely in compliance with the DMAS SOPs. DMAS approval will be sought on any divergence from the SOPs.

11.5 Documentation

Adequate documentation pertaining to the conduct of the trial will be maintained by the DMC and/or the CTPs of all stages of the data-cycle for a period specified by government agency regulations. This includes all case-report forms, source documents, recruitment and enrollment logs, consent forms, data-correction forms, error reports, data-transfer documents, data-security, regulatory documents and SOPs. Software documentation for source-code, change-control, data-extraction, report-generation should be maintained by the DMC. Requirements for physical security of study-data and other paper-documents have been specified elsewhere in this document.

11.6 Training

Nodes will provide sufficient training to research and data staff at the DMC and CTPs to ensure

[name]

their ability to meet their respective objectives for the study. This includes, but is not limited to, training in security measures, system administration, data-collection, data-entry, data-backup, documentation, and quality assurance and control, as applicable to the data model adopted by the node.

12.0 STUDY TIMETABLE

Table 4 shows the length of research and clinical training, recruitment/randomization and follow-up assessments. Numbers in the table refer to expected rates per month/per CTP.

If the case flow at a CTP is less than or greater than the rate shown in Table 4 the overall length of the study at a CTP will also be influenced.

TABLE 4. STUDY TIMETABLE

MONTHS:	1	2	3	4	5	6	7	8	9	10	11	12	13	14	15	16	17	18	19	20	21	22	23	24	25	26	27	28	29	30	31	32	33	34	35	
Outpatient																																				
Training -- Research				x																																
Training -- Clinical	x	x	x	x	x																															
B1& Randomization						5	5	5	5	5	5	5	5	5	5	5																				
T4										5	5	5	5	5	5	5	5	5	5	5																
T8														5	5	5	5	5	5	5	5	5	5	5	5											
T12																		5	5	5	5	5	5	5	5	5	5	5	5	5						
TOTAL						5	5	5	5	10	10	10	10	15	15	15	15	15	15	15	15	15	15	10	10	10	10	5	5	5	5					

13.0 DISCONTINUATION OF STUDY Interim Analyses

This trial does not meet any of the conditions listed in the Data Safety Monitoring Boards SOP that would require a planned interim analysis for efficacy:

- 1) the trial does not involve over 1000 participants
- 2) treatment is under 6 months in duration
- 3) death or other serious adverse events are not included as efficacy endpoints
- 4) published information supports the efficacy of the experimental treatment
- 5) pharmacological treatment is NOT included in the protocol

There are other factors related to this effectiveness trial's design that lessen the need for an a-priori planned interim analysis. First, this is not a blinded study. Second, the experimental treatment is being compared to the treatment as usual at each site and these sites are established drug treatment centers using established treatment approaches. It is thus highly unlikely that there will be such large effect-sizes that the trial would be stopped early due to the overwhelming efficacy of the proposed experimental treatment. On the other hand, the established research on the proposed experimental treatment does provide substantial evidence of its efficacy in treatment of adolescent problem behavior and drug abuse, making it unlikely that there would be overwhelming efficacy of the treatment as usual, over the experimental treatment. Third, the proposed estimation strategy for this trial directly accounts for the expected variability in effect size across sites by including a random effect for the treatment effect. Note that this variability is expected to be higher than might be seen in efficacy trials due to the variability in treatment as usual across sites. The stability of the statistical model is directly affected by this estimate of variability. It is generally felt that at least 5 sites are necessary to achieve a stable estimate of variability (Brown & Prescott, 1999). Because the primary test includes an interaction by modality (residential vs. outpatient), this would require at least 5 sites in each modality to generate stable estimates of the treatment effect.

For these eight reasons, and, in accordance with the Data Safety Monitoring Board's SOP, presentation of primary and secondary effectiveness outcome data and other data not intended to evaluate safety will be presented for all treatment groups combined, further broken down by study node and by CTP (when more than one CTP per node). No statistical penalty will be taken for these blinded interim analyses of efficacy data that will be conducted for the sole purpose of assessing the acceptability of safety results.

Adverse event data and other data intended for the monitoring of safety will be presented to the DSMB in an unblinded fashion. Because the trial is not powered to demonstrate statistically significant differences in adverse events or other safety outcomes, p-values will not be calculated for any differences observed unless specifically requested by members of the Board to assist in the evaluation of a potential safety concern. No adjustments will be made to the efficacy analyses for the number of interim safety analyses in the final report.

Although an interim analysis of effectiveness data is not planned, the DSMB may feel that such analysis is necessary to permit proper evaluation of safety data. Should an unscheduled interim analysis of efficacy be necessary, the Board will specify the question, the analysis required, the critical

[name]

values for a decision and the statistical procedures necessary to control the overall type 1 error at $p < 0.05$. A protocol amendment will be included in the DSMB report of the analysis describing necessary changes in the statistical plan that result from the analysis.

Should the DSMB desire that an interim analysis plan be established prior to implementation of the trial, we would recommend a single interim analysis to take place after both 1) $\frac{1}{2}$ of the subjects have completed the 8 month follow-up and 2) at least 5 sites from have enrolled some number of subjects (to ensure stability in the estimates of treatment effect variability). The trial will enroll sites “waves.”

We would further recommend, due to the lack of a compelling reason to expect overwhelming efficacy in this trial, that should an a-priori interim analysis be desired that an O’Brien-Fleming stopping boundary be used (Jennison & Turnbull, 2000). This type of boundary has the least penalty in the final test and involves the lowest inflation factor to sample size necessary to maintain power (Jennison & Turnbull, 2000; Scharfstein, Tsiatis & Robins, 1997). The critical value for the interim analysis would be 2.7959 (corresponding to a p-value of .0052), whereas the critical value for the final test would be 1.977 (corresponding to a p-value of .048). To maintain power levels the sample would need to be increased from 840 to 848.

